5. AMENDMENTS AND UPDATES

Amendment number	Date	Protocol section(s) changed	Summary of amendment(s)	Reason
1	06 December 2023	Abstract, Section 6	Revised milestones to remove the Interim Report and update the end of data collection and final study report	To align with the shortened observation period given that authorization for Pfizer-BioNTech bivalent COVID-19 Vaccine (Original and Omicron BA.4/BA.5) ended on 11 September 2023
1	06 December 2023	Section 6	Added rationale for milestone dates	Included rationale per request from the EMA
1	06 December 2023	Abstract, Section 6, Section 9.1	Updated minimum observation period from 3 years to 2 years	Due to the change in authorization of Pfizer-BioNTech bivalent COVID-19 Vaccine (Original and Omicron BA.4/BA.5) as of 11 September 2023
1	06 December 2023	Abstract, Section 6, Section 9.1, Section 12	Removed all references to interim analysis	Given the shortened observation period, only monitoring and final reports will be implemented
1	06 December 2023	Abstract, Section 7	Added information relating to Pfizer-BioNTech bivalent COVID-19 Vaccine (Original and Omicron BA.4/BA.5) no longer being authorized as of 11 September 2023	To align with regulatory updates
1	06 December 2023	Abstract, Section 9.1, Section 9.3.2.2, Section 9.3.3 Section 9.7	Removed references to analysis relating to exploring other formulations of Pfizer-BioNTech COVID-19 Vaccines	To focus the study on Pfizer-BioNTech bivalent COVID-19 Vaccine (Original and Omicron BA.4/BA.5) only
1	06 December 2023	Abstract, Section 9.1	Added feasibility during the monitoring analysis to assess uptake in women who may have been exposed during pregnancy	To assess potential study size for final analysis
1	06 December 2023	Section 9.1, Section 9.2	Added clarification that washout period would be applied for assessment of safety events	To clarify intent to identify incident cases
1	06 December 2023	Section 9.5	Added study size for pregnancy analyses (this is a newly added section (9.5.2) and the existing wording is now presented under section 9.5.1)	Per request from the EMA

090177e19f732934\Approved\Approved On: 14-Dec-2023 13:35 (GMT)

PFIZER CONFIDENTIAL

Amendment number	Date	Protocol section(s) changed	Summary of amendment(s)	Reason
1	06 December 2023	Section 9.9	Minor updates	Minor updates
1	06 December 2023	Abstract, Section 9.7.1	Add “another appropriate statistical method” as option for estimating incidence rate ratios of general safety events	To allow flexibility with method within a distributed network
1	06 December 2023	Sections 10.4 and 12	Minor editorial changes	Minor editorial changes

COVID-19 = coronavirus disease 2019; EMA = European Medicines Agency.

090177e19f732934\Approved\Approved On: 14-Dec-2023 13:35 (GMT)

6. MILESTONES

Below is the anticipated schedule of milestones, based on the anticipated data lags and timing of data availability for the planned data sources.

Milestone	Planned date
Registration in the EU PAS Register	Prior to the start of data collection
Start of data collection	30 September 2024
Monitoring analysis report	31 January 2025
End of data collection	31 July 2026
Final study report	31 January 2027

EU PAS Register = European Union electronic register of post-authorization studies

Planned dates for the study milestones are based on anticipated data lag in the data sources and a minimum of 2 years of observation (data through at least 30 August 2024) after the initial EUA of Pfizer-BioNTech bivalent (BNT162b2 and BNT162b2 OMI BA.4/BA.5) COVID-19 Vaccine, which occurred on 31 August 2022 in the US. It is anticipated that the milestone dates would allow for at least 1 year of follow-up for general safety events of interest after the Pfizer-BioNTech bivalent COVID-19 Vaccine was no longer authorized as well as least 1 year of follow-up for infants born to pregnant women receiving the Pfizer-BioNTech bivalent COVID-19 Vaccine.

The start of data collection (30 September 2024) is equivalent to the query distribution by the coordinating center (Harvard Pilgrim Health Care Institute) to participating Research Partners for the monitoring analysis, with a monitoring analysis report milestone date of 31 January 2025. Query distribution for the final analysis is anticipated to occur in the second quarter of 2026. The exact timing of query distribution will take into consideration latest data refreshes for participating research partners, which occur on a regular but staggered basis. The end of data collection (31 July 2026) is anticipated to be the date on which all analysis is complete.

7. RATIONALE AND BACKGROUND

On 31 August 2022, the US FDA authorized Pfizer-BioNTech bivalent COVID-19 Vaccine (Original and Omicron BA.4/BA.5) for emergency use as a single booster dose for the prevention of COVID-19 (coronavirus disease 2019) in individuals aged 12 years and older (FDA, 2023b). On 12 October 2022, the FDA subsequently authorized the vaccine for use as a single booster dose in individuals aged 5-11 years. Additionally, on 08 December 2022, the FDA authorized Pfizer-BioNTech bivalent COVID-19 Vaccine to be used as a third dose in the primary series in children aged 6 months through 4 years, following 2 doses of Pfizer-BioNTech monovalent COVID-19 Vaccine (Original). On 14 March 2023, the FDA authorized Pfizer-BioNTech bivalent COVID-19 Vaccine for use as a single booster dose in children aged 6 months through 4 years who had previously completed a 3-dose primary series of Pfizer-BioNTech monovalent COVID-19 Vaccine (FDA, 2023a).

PFIZER CONFIDENTIAL

CT24-WI-GL02-RF02 4.0 Non-Interventional Study Protocol Template For Secondary Data Collection Study

01-Jun-2022

Page 20 of 62

On 18 April 2023, the FDA amended the EUA for Pfizer-BioNTech COVID-19 Vaccine to simplify the vaccination schedule, such that the current bivalent vaccine was to be used for all initial and subsequent doses administered to individuals aged 6 months and older. At the same time, the original Pfizer-BioNTech monovalent COVID-19 Vaccine was no longer authorized for use (FDA, 2023b). Updates to simplify the vaccination schedule were as follows:

- For unvaccinated individuals, Pfizer-BioNTech bivalent COVID-19 Vaccine was authorized as a 3-dose series in individuals aged 6 months through 4 years and as a single dose in individuals aged 5 years and older.
- For individuals aged 6 months through 4 years who had previously received 1 dose of monovalent vaccine, Pfizer-BioNTech bivalent COVID-19 Vaccine was authorized to be used as 2 additional doses; for individuals aged 6 months through 4 years who had received 2 or 3 doses of monovalent vaccine, Pfizer-BioNTech bivalent COVID-19 Vaccine was authorized to be used as a single dose.
- For individuals aged 5 years and older who had previously received 1 or more doses of monovalent COVID-19 vaccine, a single dose of Pfizer-BioNTech bivalent COVID-19 Vaccine was authorized.
- For individuals aged 65 years and older and immunocompromised individuals aged 5 years and older, a single additional dose of Pfizer-BioNTech bivalent COVID-19 Vaccine was authorized after receipt of a first dose of bivalent COVID-19 vaccine.
- Additional doses of Pfizer-BioNTech bivalent COVID-19 Vaccine were authorized to be administered, at the discretion of the healthcare provider, taking into consideration the individual's clinical circumstances.

Additionally, on 28 April 2023, the FDA authorized the use of a fourth dose of Pfizer-BioNTech COVID-19 bivalent COVID-19 Vaccine for immunocompromised individuals aged 6 months through 4 years who had previously received 3 doses of Pfizer-BioNTech monovalent COVID-19 Vaccine or Pfizer-BioNTech bivalent COVID-19 Vaccine. Myocarditis and pericarditis were included in the warnings and precautions of the EUA factsheet for the Pfizer-BioNTech COVID-19 Vaccine, Bivalent (Original and Omicron BA.4/BA.5), stating “Post-marketing safety data with Pfizer-BioNTech COVID-19 Vaccine are relevant to Pfizer-BioNTech COVID-19 Vaccine, Bivalent because these vaccines are manufactured using the same process. Post-marketing data with authorized or approved monovalent mRNA COVID-19 vaccines demonstrate increased risks of myocarditis and pericarditis, particularly within the first week following vaccination. For the Pfizer-BioNTech COVID-19 Vaccine, the observed risk is highest in males 12 through 17 years of age. Although some cases required intensive care support, available data from short-term follow-up suggest that most individuals have had resolution of symptoms with conservative management. Information is not yet available about potential long-term sequelae” (FDA, 2023a).

PFIZER CONFIDENTIAL

As of 11 September 2023, the Pfizer-BioNTech bivalent COVID-19 Vaccine (Original and Omicron BA.4/BA.5) is no longer authorized for use in the US (since the updated [2023–2024 Formula] COVID-19 Pfizer-BioNTech COVID-19 Vaccine became available) (Regan et al., 2023). Since the authorization of Pfizer-BioNTech bivalent COVID-19 Vaccine, no safety signal for myocarditis/pericarditis has been observed with this vaccine in any age group in the VSD, with preliminary data suggesting lower rates of myocarditis/pericarditis following booster vaccination with Pfizer-BioNTech bivalent COVID-19 Vaccine compared with rates of myocarditis/pericarditis following receipt of Pfizer-BioNTech monovalent COVID-19 Vaccine among individuals aged 12-39 years (Shimabukuro, 2023). While a potential safety signal for ischemic stroke for individuals aged 65 years and older was initially observed in the VSD, the signal was not subsequently confirmed (Shimabukuro, 2023).

Post-authorization observational studies using real-world data are still needed among the general population and among subpopulations of interest (eg, pregnant people, immunocompromised individuals, and the pediatric population) to assess the association between Pfizer-BioNTech bivalent COVID-19 Vaccine and pre-determined safety events of interest, including myocarditis/pericarditis. This protocol describes a proposed observational study of safety events of interest, including myocarditis/pericarditis, occurring in recipients of the Pfizer-BioNTech bivalent COVID-19 Vaccine using claims data and electronic health records data (where available) from data RPs participating in the FDA Sentinel System.

This non-interventional study is designated as a Post-Authorization Safety Study (PASS) and is a commitment to the US FDA and is also a RMP Category 3 commitment to the EMA.

8. RESEARCH QUESTION AND OBJECTIVES

Research questions

1. What is the incidence of safety events of interest (including myocarditis/pericarditis) following receipt of Pfizer-BioNTech bivalent COVID-19 Vaccine as compared with a self-matched control interval?
2. What is the incidence of pregnancy outcomes (including spontaneous abortion, stillbirth, and preterm birth) following receipt of Pfizer-BioNTech bivalent COVID-19 Vaccine during pregnancy compared with no receipt of any COVID-19 vaccine during pregnancy?
3. What is the prevalence of birth outcomes (including major congenital malformations and small size for gestational age) in infants born to women who were exposed to Pfizer-BioNTech bivalent COVID-19 Vaccine during pregnancy compared with that in infants born to women who were not exposed to any COVID-19 vaccine during pregnancy?

Primary objectives

1. To estimate the relative risk of safety events of interest (including myocarditis/pericarditis) in a post-vaccination risk interval, compared with a self-matched post-vaccination control interval, among individuals in the overall population who have received Pfizer-BioNTech bivalent COVID-19 Vaccine.

PFIZER CONFIDENTIAL

CT24-WI-GL02-RF02 4.0 Non-Interventional Study Protocol Template For Secondary Data Collection Study

01-Jun-2022

Page 22 of 62

2. To estimate the relative risk of pregnancy outcomes (including spontaneous abortion, stillbirth, and preterm birth) following receipt of Pfizer-BioNTech bivalent COVID-19 Vaccine during pregnancy compared with no receipt of any COVID-19 vaccine during pregnancy.
3. To estimate the POR of birth outcomes (including major congenital malformations and small size for gestational age) in infants born to women who were exposed to Pfizer-BioNTech bivalent COVID-19 Vaccine during pregnancy compared with that in infants born to women who were not exposed to any COVID-19 vaccine during pregnancy.

Secondary objectives

1. To estimate the relative risk of safety events of interest (including myocarditis/pericarditis) in a post-vaccination risk interval, compared with a self-matched post-vaccination control interval, among individuals who have received Pfizer-BioNTech bivalent COVID-19 Vaccine for the following subgroups: pregnant women, immunocompromised individuals, individuals with a recorded history of severe COVID-19, and subgroups defined by age (as appropriate for the outcome).
2. To estimate the relative risk of pregnancy outcomes (including spontaneous abortion, stillbirth, and preterm birth) following receipt of Pfizer-BioNTech bivalent COVID-19 Vaccine during pregnancy compared with no receipt of any COVID-19 vaccine during pregnancy by subgroups of maternal age.
3. To estimate the POR of birth outcomes (including major congenital malformations and small size for gestational age) in infants born to women who were exposed to Pfizer-BioNTech bivalent COVID-19 Vaccine during pregnancy compared with that in infants born to women who were not exposed to any COVID-19 vaccine during pregnancy by subgroups of maternal age.

9. RESEARCH METHODS

9.1. Study design

The study will use a SCRI design to assess general safety events (ie, non-pregnancy related safety events of interest, including myocarditis/pericarditis; see Section 9.3.2.1 for list of specific events) among the general population and specific subpopulations of interest (immunocompromised individuals, pregnant women, and the pediatric population). A cohort design will be used to assess pregnancy and birth outcomes.

For general safety events, the SCRI design (Figure 1) will compare the incidence of safety events of interest in a predefined post-vaccination risk interval with that in a self-matched post-vaccination control interval, among individuals who have received Pfizer-BioNTech bivalent COVID-19 Vaccine. A buffer period (in which incidence will not be assessed) will be incorporated between the risk and control intervals to avoid any carry over effects from the risk interval into the control interval. Control intervals for each outcome will be defined to reflect the baseline risk of the outcome, and buffer and control intervals will take into consideration the duration of the risk interval, potential seasonality of the outcome, and the recommended timing between the initial bivalent vaccine dose and additional COVID-19

[figure not shown]
PFIZER CONFIDENTIAL

CT24-WI-GL02-RF02 4.0 Non-Interventional Study Protocol Template For Secondary Data Collection Study
01-Jun-2022

Page 23 of 62

vaccine doses. Additionally, as an eligibility criterion for each specific safety event of interest, a set period of time prior to the event date (washout period) in which the individual may not have experienced the safety event of interest will be defined to more plausibly identify incident cases.

Figure 1. Self-controlled risk interval design to assess general safety events

[figure not shown]
COVID-19 = coronavirus disease 2019.

This study design is appropriate for studying acute events with well-defined risk periods. A strength of the SCRI design is that it avoids confounding due to time-invariant confounders (including prior history of COVID-19 vaccination, which may be challenging to identify in claims administrative data). Additionally, because the SCRI design only includes vaccinated individuals, it avoids misclassification of unexposed status arising from incomplete capture of COVID-19 vaccination in claims data.

Among pregnant women, a cohort design will be used to compare the incidence of pregnancy outcomes (spontaneous abortion, stillbirth, and preterm birth) among those who were exposed to Pfizer-BioNTech bivalent COVID-19 Vaccine during pregnancy compared with that among those who were unexposed to any COVID-19 vaccine during pregnancy (Figure 2). Similarly, a cohort design will be used to compare the prevalence of birth outcomes (major congenital malformations and small size for gestational age) in infants who were born to pregnant women who were exposed to Pfizer-BioNTech bivalent COVID-19 Vaccine during pregnancy compared with that in infants born to pregnant women who were unexposed to any COVID-19 vaccine during pregnancy (Figure 3). Exposed and unexposed pregnant women will be matched on estimated pregnancy start (date of last menstrual period [LMP]), gestational age at cohort entry (for pregnancy outcomes only), maternal age, and US state (if feasible, or broader geographic region if not feasible). Inverse probability of treatment weighting will be used to account for additional confounders.

[figure not shown]
090177e19f732934\Approved\Approved On: 14-Dec-2023 13:35 (GMT)

Figure 2. Cohort design to assess pregnancy outcomes

COVID-19 = coronavirus disease 2019; LMP = date of last menstrual period.

Figure 3. Cohort design to assess birth outcomes

COVID-19 = coronavirus disease 2019; LMP = date of last menstrual period.

A strength of a cohort design with concurrent unexposed comparators is that, unlike the SCRI design, it can be used to study safety events for which the risk varies substantially over time (such as spontaneous abortion) and/or for which the timing of onset is unknown (such as major congenital malformations and small size for gestational age). The use of a contemporaneous comparator rather than a historical comparator avoids bias due to temporal trends in coding for outcomes. Limitations of the cohort approach include the potential for bias due to misclassification of exposed individuals as “unexposed” comparators and bias due to confounding when comparing exposed with unexposed pregnant women.

Confounding will be handled by matching and inverse probability of treatment weighting.

To assess the feasibility for planned analyses, a monitoring analysis will be conducted to describe vaccine utilization among the overall population, among immunocompromised

individuals, among individuals with a history of severe COVID-19, and in subgroups defined by age, as well as among women who may have been exposed during pregnancy (based on pregnancy markers in the 200 days before the index date).

The study period will start on the date that Pfizer-BioNTech bivalent COVID-19 Vaccine was granted EUA in the US (31 August 2022) and will end a minimum of 2 years after this date.

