9.2.2. Pregnancy outcomes (spontaneous abortion, stillbirth, and preterm birth)

Separate cohorts of pregnant women exposed to Pfizer-BioNTech bivalent COVID-19 Vaccine (exposed cohort) and pregnant women not exposed to any COVID-19 vaccine (unexposed cohort) will be formed for the final analysis of pregnancy outcomes (Table 1). To be eligible for either cohort, pregnant women must be enrolled from 12 months before cohort entry (ie, the index date) until the end of pregnancy.

Table 1. Cohort definitions for analysis of pregnancy outcomes

Cohort	Eligibility criteria	Index date
Exposed cohort	
 Receipt of a dose of Pfizer-BioNTech bivalent COVID-19 Vaccine in the exposure window (as defined in Table 3) Continuous enrollment in the 12 months before the index date until end of pregnancy 	
 Date of vaccination
Unexposed cohort	
 No receipt of any COVID-19 vaccine in the exposure window (as defined in Table 3) Continuous enrollment in the 12 months before the index date until end of pregnancy Matched individually (in a ratio of at least 1:1) to exposed women on estimated pregnancy start (LMP, within pre-specified calendar intervals), maternal age, and US state (if feasible, or broader geographic region if not feasible) 	
 Equivalent of the gestational age at vaccination (in days) in the exposed match. For example, if an exposed individual was vaccinated at 28 weeks and 3 days of gestation, the index date for unexposed matches would be set to 28 weeks and 3 days after their LMP.

COVID-19 = coronavirus disease 2019; LMP = date of last menstrual period; US = United States.

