9.2.3. Birth outcomes (major congenital malformations and small size for gestational age)

Separate cohorts of pregnant women exposed to Pfizer-BioNTech bivalent COVID-19 Vaccine (exposed cohort) and pregnant women not exposed to any COVID-19 vaccine (unexposed cohort) will be formed for the analysis of birth outcomes (Table 2). To be eligible for either cohort, women must have had a singleton pregnancy ending in a livebirth and must have had continuous enrollment from 12 months before the index date until birth. The index date in both exposed and unexposed women will be the LMP date. Analyses will be limited to pregnant women whose singleton pregnancies have ended in a livebirth and who have been successfully linked to an infant.

Table 2. Cohort definitions for analysis of birth outcomes

Cohort	Eligibility criteria
Exposed cohort	
 Pregnancy ending in a livebirth, with continuous enrollment in the 12 months before the index date (LMP) until birth Pregnancy linked to at least 1 infant Receipt of Pfizer-BioNTech bivalent COVID-19 Vaccine during the outcome-specific exposure window (as defined in Table 3)
Unexposed cohort	
 Pregnancy ending in a livebirth, with continuous enrollment in the 12 months before the index date (LMP) until birth Pregnancy linked to at least 1 infant

PFIZER CONFIDENTIAL

Table 2. Cohort definitions for analysis of birth outcomes

Cohort	Eligibility criteria
	
 No receipt of any COVID-19 vaccine during the outcome-specific exposure window (as defined in Table 3) Matched individually (in a ratio of at least 1:1) to exposed women on LMP, maternal age, and US state (if feasible, or broader geographic region if not feasible)

COVID-19 = coronavirus disease 2019; LMP = date of last menstrual period. US = United States

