9.2.3.1. Exposure windows for analyses in pregnant women

Outcome-specific exposure windows are provided in Table 3. For pregnancy and birth outcomes, only women who were exposed to Pfizer-BioNTech bivalent COVID-19 Vaccine during outcome-specific exposure windows will be eligible for the exposed cohorts. For each pregnancy and birth outcome, the exposure window will be from 28 days before pregnancy start until the end of the outcome-specific risk period (as defined in [Section 9.3.2.2](#)).

Table 3. Exposure windows for analysis of pregnancy outcomes and birth outcomes

Type of safety event	Safety event of interest	Exposure window
Pregnancy outcomes	Spontaneous abortion	From 28 days before LMP until 19 weeks and 6 days of gestation
	Stillbirth	From 28 days before LMP until pregnancy end
	Preterm birth	From 28 days before LMP until 36 weeks and 6 days of gestation
Birth outcomes	Major congenital malformations	From 28 days before LMP until the last day of the first trimester
	Small size for gestational age	From 28 days before LMP until pregnancy end

LMP = date of last menstrual period.

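### SGA comparators need not be still pregnant at the gestational age when their match was vaccinated, which can bias the SGA prevalence odds ratio, downward if coded SGA is more frequent in earlier deliveries

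*Protocol*

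**What the plan says.** For SGA, Protocol Table 3 (Section 9.2.3.1) sets the exposure window as "From 28 days before LMP until pregnancy end". For major congenital malformations the window is "From 28 days before LMP until the last day of the first trimester".

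Section 9.2.3 fixes time zero for both birth outcomes: "The index date in both exposed and unexposed women will be the LMP date". Table 2 describes the comparators as "Matched individually (in a ratio of at least 1:1) to exposed women on LMP, maternal age, and US state" (or a broader region) and requires "No receipt of any COVID-19 vaccine during the outcome-specific exposure window". Section 9.1 lists the matching factors, besides LMP, as "gestational age at cohort entry (for pregnancy outcomes only), maternal age, and US state". The gestational-age match is thus expressly switched off for birth outcomes. Both cohorts are conditioned on the same end: "Analyses will be limited to pregnant women whose singleton pregnancies have ended in a livebirth".

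For spontaneous abortion, stillbirth and preterm birth, Table 1 does align the two groups. The comparator's index date is "Equivalent of the gestational age at vaccination (in days) in the exposed match".

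**The concern.** A woman vaccinated at 36 weeks is in the exposed cohort only because she had not delivered by 36 weeks. Her SGA comparator shares her LMP interval, age and region but may have delivered at 30 weeks. More generally, a pregnancy that ends early has fewer weeks in which it could become exposed, so early deliveries are over-represented among the unexposed. If coded SGA is more frequent in early deliveries, the unexposed cohort then carries an excess of SGA that has nothing to do with the vaccine. The POR drops below its true value, and in a safety study that direction hides harm.

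SGA is part of primary objective 3, and nothing else in the plan removes the imbalance. Table 7 (footnotes b and d) restricts time-dependent propensity score information to the period up to the index date, apart from multiple pregnancy. That date is LMP here, so neither vaccination timing nor length of gestation can enter. The sensitivity analyses (Section 9.7.3) and the limitations (Section 9.9) do not mention the problem.

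**Working it through.** **1. The plan's own figure.** Section 9.5.2 gives 90% power for birth outcomes at OR 1.2, 3% in the unexposed, 20,000 per group and two-sided 0.05. The exposed odds are 1.2 × 0.03/0.97 = 0.03711, so the exposed prevalence is 0.03579. The SE of the log OR is √[1/(20,000 × 0.03 × 0.97) + 1/(20,000 × 0.03579 × 0.96421)] = 0.0563. Power = Φ(ln 1.2/0.0563 − 1.96) = Φ(1.28) = 0.90. The figure reproduces, and the point does not depend on it.

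**2. Effect of the matching rule on length of gestation.** Inputs: 10% preterm (Section 9.5.2). Assumed, because the documents give no figure: a spread of births over weeks 22 to 42, 10% SGA overall, 10% vaccinated among pregnancies lasting through the whole vaccination period, timing uniform within that period, and no vaccine effect. The preterm shares that result are:
- vaccination over weeks −4 to 42: 8.94% exposed, 10.11% unexposed;
- vaccination over weeks 27 to 40 only: 6.37% exposed, 10.36% unexposed.

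**3. From length of gestation to POR.** Let R be the ratio of SGA prevalence in preterm to term births, and q a cohort's preterm share. Term prevalence is t = 0.10/(0.9 + 0.1R), and cohort prevalence is t[1 + (R − 1)q].

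Example, R = 2, weeks −4 to 42: t = 0.10/1.1 = 0.0909. Exposed: 0.0909 × 1.0894 = 0.0990. Unexposed: 0.0909 × 1.1011 = 0.1001. POR = (0.0990/0.9010)/(0.1001/0.8999) = 0.988.

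| R | Weeks −4 to 42 | Weeks 27 to 40 |
|---|---|---|
| 0.7 | 1.004 | 1.014 |
| 1 | 1.000 | 1.000 |
| 1.5 | 0.994 | 0.979 |
| 2 | 0.988 | 0.960 |
| 3 | 0.979 | 0.927 |

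With 30% vaccinated instead of 10%, the bottom row becomes 0.973 and 0.911. If vaccination stops at week 13, the POR is 1.000 for every R, so the malformation analysis is unaffected.

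**4. Simulation.** This used 3 million pregnancies per scenario, 10% preterm, 10% SGA, a constant vaccination hazard giving 12% uptake by day 280, and no true effect. The standard error of each log OR is about 0.006, and repeat runs differ by up to about 0.02.
- Vaccination across the window, R from 1.5 to 3: POR about 0.98 to 0.99.
- The same, with SGA infants also delivered 7 to 10 days earlier: about 0.95 to 0.97.
- All vaccination after 28 weeks: about 0.92 to 0.98.
- All vaccination after 28 weeks, plus earlier delivery: about 0.81 to 0.86.

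**5. With comparators required to be still pregnant** at the match's vaccination age, the POR returns to about 0.98 to 1.01 in these scenarios. A remainder persists because comparators must also stay unvaccinated until delivery.

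**6. Scale.** At 10% SGA and 20,000 per group, the null SE of the log OR is √[2/(20,000 × 0.10 × 0.90)] = 0.033. The 95% limits around 1 are therefore exp(±0.065), or 0.94 to 1.07. A bias to 0.98 or 0.99 lies well inside random error, and one to 0.95 is close to its edge. At the planning rate of 3%, a 5% downward bias turns OR 1.2 into 1.14, and power becomes Φ(ln 1.14/0.0569 − 1.96) = Φ(0.34) = 0.63. At 10% SGA it would be Φ(ln 1.14/0.0325 − 1.96) = Φ(2.07) = 0.98.

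**The case against.** The strongest objection concerns direction. Table 6 defines SGA as low weight for gestational age, so the outcome is already standardised to length of gestation, and both cohorts consist of live births. Unequal gestation can then bias the POR only if SGA frequency varies with gestational age at delivery. A reader might infer that the POR must fall below the truth. The documents do not support that: they give no SGA frequency by gestational age, and the bias is zero at R = 1 and slightly upward at R = 0.7. This objection stands, and the point is therefore conditional.

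A reader might also take the values of 0.81 to 0.86 as the expected size. They need every vaccination to fall after 28 weeks and SGA infants to deliver 7 to 10 days early. The window opens 28 days before LMP, and nothing in the protocol suggests uptake confined to the third trimester. The calendar does force late exposure on some pregnancies: with LMP before 16 February 2022, 28 weeks (196 days) had passed by authorization on 31 August 2022. But requiring the pregnancy outcome to fall in the study period already excludes their deliveries before that date. Conversely, pregnancies with LMP after 27 February 2023 had not reached 28 weeks when authorization ended on 11 September 2023. The all-late scenario is an extreme, not a forecast.

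Calling this immortal time is also loose. SGA is a prevalence outcome analysed by logistic regression, and no person-time is misallocated. The problem is unequal opportunity for exposure. These corrections limit the size and direction of the bias; they do not supply the missing alignment.

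**Conclusion.** The gap in the matching rule is written into Sections 9.1 and 9.2.3 and is not a detail left open for the SAP. It affects SGA only. It can bias the SGA POR, and the direction depends on how coded SGA varies with gestational age at delivery, which the protocol does not state.

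If SGA is 1.5 to 3 times as common in preterm births, the downward bias is about 1% to 2% with vaccination spread over the window. It is about 3% to 5% if SGA infants also deliver 7 to 10 days earlier, and larger only if vaccination is all late. All of these rest on assumed SGA prevalence, uptake, timing and spread of births. The likely size is modest beside the planning odds ratio of 1.2. The change is still worth making, because the plausible direction hides harm and the protocol already uses the remedy for the pregnancy outcomes.

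**What to change.** For SGA only, require each comparator to be still pregnant and unvaccinated at the gestational age at which her match was vaccinated, following the Table 1 rule. Keep LMP-only matching for major congenital malformations.

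This takes more than one sentence. Section 9.1 and Table 2 need an SGA-specific matching rule. Table 7 footnote c, which confines gestational age on the index date to pregnancy outcomes, needs amending, as does the parallel remark in the abstract. Because Table 1 ties the comparator's index date to the match's vaccination, the text must also say whether LMP remains the covariate cut-off for the SGA propensity score.

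The cost is slightly fewer eligible comparators for late vaccinations. A small residual bias remains (POR about 0.98 to 1.01 under no effect) as long as comparators must stay unvaccinated to delivery, and Section 9.9 should say so.
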